9.9.2. Neurologic Function

Neurologic function will be measured using the NIHSS.

10. OTHER ASSESSMENTS

Functional outcome will be assessed using mRS.

11. STATISTICAL METHODS

Detailed statistical methods will be described in a Statistical Analysis Plan or data analysis plan. The analysis plan will be finalized prior to database lock.

11.1. Analysis Sets

The following analysis sets will be used during this study:

The randomized analysis set will include all subjects who signed (or signed by their legally acceptable representative) the ICF and were randomized into the study.

The safety analysis set will include all subjects who received at least 1 dose of investigational product.

The PK analysis set will include all subjects who received a dose of DS-1040b and have sufficient plasma concentration data for DS-1040a to characterize the PK parameters.

The PD analysis set will include all subjects who received a dose of study medication and have at least 1 postdose PD assessment.

11.2. General Statistical Considerations

The primary analysis is to assess the safety and tolerability of DS-1040b in subjects with AIS.

In all the analyses, data will be tabulated with descriptive summary statistics for exploratory and hypothesis-generating purpose. No imputation will be performed for dropouts or missing data.

All quantitative PK, PD, and safety data will be tabulated with descriptive summary statistics: arithmetic mean; standard deviation (SD); median, minimum and maximum values; number of observations. In addition, geometric mean and the coefficient of variation (%CV) for geometric mean will also be calculated for AUC_{0-inf} , AUC_{last} , and C_{max} . Frequency counts and percentages will be provided for categorical data. Summaries will be provided for each active dose arm and on the pooled placebo arm. When data are available for both predose and postdose assessments, summaries will be provided on predose assessments, postdose assessments, and change from predose to postdose assessments, respectively.

Results from placebo-treated subjects will be pooled across cohorts

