2.1.2. Secondary Objectives

The secondary objectives of the study are as follows:

- To assess the plasma and urinary PK of DS-1040b in subjects with AIS.
- To assess the effect of DS-1040b on fibrinolysis biomarkers in subjects with AIS.
- To assess the effect of DS-1040b on recanalization at 24 hours in subjects with AIS.
- To assess the effect of DS-1040b on neurological outcome by using the National Institute of Health Stroke Scale (NIHSS) and functional outcome by using the modified Rankin Scale (mRS) in subjects with AIS.

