4.2. Removal of Subjects From Therapy

4.2.1. Reasons for Withdrawal/Early Discontinuation

Any subject who discontinues from study treatment for any reason will have their study treatment discontinuation recorded.

Subjects may be withdrawn from the study after signing informed consent for the following reasons:

- Adverse event
- Lost to follow up
- Death
- Protocol violation
- Withdrawal of consent by subject
- Study terminated by Sponsor
- Other (eg, discretion of the Investigator)

If a subject withdraws from the study, the Investigator will complete and report the observations as thoroughly as possible up to the date of withdrawal including the date of last treatment and the reason for withdrawal.

If the subject is withdrawn due to an adverse event, the Investigator will follow the subject until the adverse event has resolved or stabilized.

All subjects who are withdrawn from the study should complete protocol-specified withdrawal procedures (Section 4.2.2).

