6.5. Day 5 (Early Discharge or Discontinuation)

The following activities and/or assessments will be performed on Day 5 (96 hours after dosing):

- Perform a complete physical examination
- Record prior/concomitant medication
- Administer the NIHSS
- Administer the mRS
- Assess subjects for adverse events
- Obtain PK blood sample

Attempts should be made to complete all assessments during this visit for subjects who withdraw from the study. After discharge, no further assessments are required until the Day 30 Follow-up Visit.

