6.6. Follow-up

6.6.1. Day 30

The following activities and/or assessments will be performed on Day 30 \pm 7 days:

- Perform a complete physical examination
- Administer the NIHSS
- Administer the mRS
- Assess subjects for adverse events

6.6.2. Day 90

The following activities and/or assessments will be performed on Day 90 ± 7 days:

- Administer the mRS
- Assess subjects for adverse events

This visit will occur as a phone contact.

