11.6.6.2. Neurologic function

Neurologic function will be assessed using the NIHSS. Raw values of the NIHSS score will be presented graphically by subject, and will also be summarized by treatment. Change from baseline values will be summarized. The number and percentage of subjects of 0 or 1 point of postdose NIHSS and 4 points or more improvement of NIHSS will be tabulated by scheduled time of evaluation and treatment. Pooled placebo data of all cohorts will be summarized.

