11.7. Other Analyses

Functional outcome will be assessed using the mRS. Raw values of mRS scores will be presented graphically by subject, and will also be summarized by treatment. Change from baseline values (inclusion/exclusion criteria) will be summarized. The number and percentage of subjects of 0 or 1 point of postdose mRS will be tabulated by scheduled time of evaluation and treatment. Pooled placebo data of all cohorts will be summarized.

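### The no-imputation rule makes no exception for death: NIHSS means cover survivors only, chiefly at Day 30, and NIHSS responder percentages rest on an unstated denominator

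*Combined protocol and SAP*

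**What the plan says.** Section 11.2 of the combined protocol and SAP describes every analysis as descriptive and then gives a single missing-data rule: "No imputation will be performed for dropouts or missing data". It makes no exception for death. Section 4.2.1 opens its list of withdrawal reasons with "Subjects may be withdrawn from the study after signing informed consent for the following reasons", and death stands on that list beside loss to follow-up and withdrawn consent. Under Section 4.2.3, subjects who leave early are not replaced.

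Section 11.6.6.2 summarises NIHSS scores and their change from baseline. It then tabulates, for each visit and treatment, "The number and percentage of subjects of 0 or 1 point of postdose NIHSS and 4 points or more improvement of NIHSS". It states no denominator and assigns no value or category to a subject who has died. Section 11.7 does the same for function: "The number and percentage of subjects of 0 or 1 point of postdose mRS will be tabulated by scheduled time of evaluation and treatment".

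NIHSS is taken before dosing, at 6 and 24 hours, at Day 5 (or at discharge if that comes sooner) and at Day 30. Section 2.1.2 makes NIHSS and mRS outcome a secondary objective. Section 11 leaves the detail open: "Detailed statistical methods will be described in a Statistical Analysis Plan or data analysis plan".

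**The concern.** A subject who has died has no NIHSS score. If death is handled as just another dropout, the subject leaves the table in the same way as someone who missed a visit. Death is itself an outcome, and a bad one, so dropping it can make a dose with more deaths look neurologically better than it was.

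The trial has no hypothesis tests, so these tables are how the secondary objective on neurological outcome will be read, dose by dose against pooled placebo. The plan sets stopping rules for symptomatic intracranial hemorrhage (Section 3.1.6), so fatal outcomes are foreseeable.

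**Working it through.** **1. What follows from the text alone.** Section 11.2 covers dropouts in all analyses, Section 4.2.1 includes death among withdrawals, and Sections 11.6.6.2 and 11.7 add no death rule. Means and changes from baseline can then use only subjects alive and scored at the visit. No assumption is needed for this.

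**2. Which visits are exposed.** Section 6.5 and footnote b of Section 17.5 move the Day 5 assessments forward to discharge, which may come at any time after 24 hours. A subject who dies after discharge has already given that score, so only earlier deaths are lost there. Day 30 loses every death up to that visit. The 6-hour and 24-hour summaries have the same gap for very early deaths.

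**3. Responder percentages.** The plan has no figure to reproduce, because it gives neither a death rate nor a response rate. The inputs are:
- Active subjects per dose: 12 in Cohorts 3 to 5, and 6 in Cohorts 1 and 2 if not expanded (Table 3.1).
- Deaths per dose group, d: assumed to be 1 or 2.
- Responders, r: assumed values, for illustration.
- All survivors assessed, except in step 5.

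With observed cases as denominator the percentage is r/(n − d). With deaths counted as non-response it is r/n. The ratio is n/(n − d), whatever the value of r:

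| n | d | n/(n − d) |
|---|---|---|
| 12 | 1 | 12/11 = 1.09 |
| 12 | 2 | 12/10 = 1.20 |
| 6 | 1 | 6/5 = 1.20 |
| 6 | 2 | 6/4 = 1.50 |

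If the denominator is all dosed subjects, the percentage is r/n and the factor is 1.00: deaths cause no inflation.

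**4. Absolute shift.** This depends on the response rate:
- r = 5, n = 12, d = 1: 5/12 = 41.7% becomes 5/11 = 45.5%, a shift of 3.8 points.
- r = 5, n = 12, d = 2: 5/12 = 41.7% becomes 5/10 = 50.0%, a shift of 8.3 points.
- r = 10, n = 12, d = 2: 10/12 = 83.3% becomes 10/10 = 100%, a shift of 16.7 points.

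For scale, the standard error of 5/12 is √(0.4167 × 0.5833/12) = 0.142, or about 14 points.

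**5. Why all dosed is not the best denominator either.** Take 12 dosed, 2 deaths, 1 living subject not assessed and 5 responders:
- Observed cases: 5/9 = 55.6%.
- Assessed plus deaths: 5/(9 + 2) = 5/11 = 45.5%.
- All dosed: 5/12 = 41.7%.

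The last figure counts the living subject without a score as a failure, which is imputation in effect. The middle one counts the deaths and leaves the living subject unimputed.

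**6. How likely a death is.** At an assumed 30-day mortality q, the chance of at least one death among 12 is 1 − (1 − q)^12. That is 46% at q = 5% and 93% at q = 20%.

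**The case against.** The strongest reply is that the inflation depends on a denominator the plan never chose. NIHSS is analysed under safety, and Section 11.1 defines the safety set as everyone dosed. On that denominator a death is already a non-response. This stands: a reader might infer that the responder percentages are certain to be inflated, and the documents do not support that. They leave observed cases and all dosed both open, and the two give different answers.

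Other parts of the reply also stand:
- A reader might treat Day 5 and Day 30 as equally exposed. The discharge provision rules that out.
- A reader might take 8.3 points as a ceiling. It belongs to the example with 5 responders.
- A reader might conclude that mRS is mishandled in the same way. The documents do not list the mRS categories, so whether the scale already scores death cannot be settled from them.
- The direction of bias is shown only for observed-case percentages, not for means or changes.

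It can also be said that efficacy is not evaluated (Sections 7 and 11.4), that withdrawals and their reasons are summarised (Section 11.3), that deaths are listed (Section 11.6.1), and that a later analysis plan may fill the gap. These points limit the consequence but do not remove it. Section 2.1.2 still promises an assessment of neurological outcome. The separate listings do not change the NIHSS tables, and a smaller number of observations does not tell a death from a missed visit. Section 11.2 already fixes a rule that the later plan would inherit.

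**Conclusion.** The point holds in limited form. As written, the plan makes NIHSS means and changes survivor-only, mainly at Day 30, and leaves it open whether deaths drop out of the responder percentages.

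If observed cases are used and every survivor is assessed, the inflation for 1 or 2 deaths is 1.09 to 1.20 with 12 active subjects and 1.20 to 1.50 with 6. If all dosed subjects are used, deaths cause none. The death and responder counts are assumptions, because the documents give none.

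The consequence is confined to descriptive, hypothesis-generating summaries. A reader might infer that dose escalation is compromised or that doses would be misranked. Neither follows: the escalation criteria in Section 3.1.6 do not use these tables, and in the 5-of-12 example the shift lies within one standard error. The change is still worth making, since counting deaths is a better method and the data are already collected.

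**What to change.** - **Sections 11.2 and 11.6.6.2:** except death from the no-imputation rule. Count it as non-response in the tables of NIHSS 0 to 1 and of improvement by 4 points or more. The denominator is subjects assessed at the visit plus those who died by then.
- **Living subjects without a score:** leave them unimputed and show their number at each visit.
- **NIHSS means and changes:** label them *among survivors assessed*, with the number of deaths beside them.
- **Section 11.7:** count deaths as not achieving mRS 0 to 1, on the same denominator. Do not prescribe an mRS category for death, because the documents do not list the categories.

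The analysis plan that Section 11 defers to should carry the same wording before database lock. The cost is some text and minor programming. Deaths are already captured to Day 90 through adverse event reporting (Section 9.1), so no new data are needed. The downside is that response rates become slightly less favourable where deaths occur.

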11.3. Study Population Data

Demographic characteristics will be summarized for the randomized analysis set and presented according to the treatment to which they were randomized. The number of subjects who complete the study will be presented. The timing and primary reason for withdrawal will be summarized. Inclusion of subjects in each of the defined analysis sets will also be summarized. Continuous demographic variables for all subjects will be summarized with descriptive statistics. Categorical demographic variables will be

summarized with frequency counts and corresponding percentages. Pooled placebo data of all cohorts will be summarized.

11.4. Efficacy Analyses

Not applicable.

11.5. Pharmacokinetic/Pharmacodynamic Analyses

11.5.1. Pharmacokinetic Analyses

Descriptive statistics (sample size [N], number missing [N missing], arithmetic mean, SD, %CV, minimum, maximum, and median) of DS-1040a plasma concentrations at each sampling time point and all PK parameters, including urinary PK will be presented by dose. In addition, the geometric mean and %CV for geometric mean will also be calculated for the PK parameters AUC_{0-inf} , AUC_{last} , and C_{max} .

Mean and median plasma concentration versus time data will be presented graphically for all treatments using original and semi-log scales.

Actual sampling times that differ from the scheduled sampling times by more than 5 minutes within the first hour, or by more than 30 minutes within the first 12 hours, or by more than 1 hour thereafter, will be listed but excluded from summary statistics at each timepoint and mean and median graphs.

The relationship between dose and exposure parameters (AUC_{0-inf} , AUC_{last} , and C_{max}) will be examined graphically.

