Pharmacodynamic analysis for thrombin-activatable fibrinolysis inhibitor (TAFIa) antigen, clot lysis (an exploratory biomarker), D-dimer, and total TAFIa activity will be performed. Remaining blood samples will be used for post-hoc TAFIa inhibition-related coagulation biomarker assessments.

Recanalization will be assessed by CT (or MR) angiography at baseline and 24 hours after the start of treatment using Thrombolysis in Myocardial Infarction (TIMI) criteria.

Functional Outcome Parameter:

Functional outcome will be assessed using mRS.

Statistical Analyses:

Safety Parameters:

Safety parameters will include SAEs, TEAEs, physical examination findings, vital signs measurements, standard clinical laboratory parameters, and ECG parameters.

Safety analyses in general will be descriptive and will be presented in tabular format with the appropriate summary statistics.

Values for safety assessments will be summarized by treatment group. Results from placebo-treated subjects will be pooled across cohorts.

Bleeding events will be summarized as sICH, any ICH, or non-ICH major bleeding by treatment. Results from placebo-treated subjects will be pooled across cohorts.

Neurologic function will be assessed using the NIHSS. Raw values of NIHSS scores will be presented graphically by subject, and will also be summarized by treatment. Change from baseline values will be summarized. Pooled placebo data of all cohorts will be summarized.

PK Parameters:

Descriptive statistics (sample size [N], number missing [N missing], arithmetic mean, standard deviation, coefficient of variation [%CV], minimum, maximum, and median) of

DS-1040a plasma concentrations at each sampling time point and all PK parameters, including urinary PK will be presented by treatment. In addition, the geometric mean and %CV for geometric mean will also be calculated for the PK parameters AUC_{0-inf} , AUC_{last} , and C_{max} .

Mean and median plasma concentration versus time data will be presented graphically for all treatments using original and semi-log scales.

Actual sampling times that differ from the scheduled sampling times by more than 5 minutes within the first hour, or by more than 30 minutes within the first 12 hours, or by more than 1 hour thereafter, will be listed but excluded from summary statistics and mean and median graphs.

The relationship between dose and exposure parameters (C_{max} , AUC_{last} , and AUC_{0-inf}) will be examined graphically.

PD Parameters:

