3.2. Selection of Doses

3.2.1. Experimental Treatments

This study will enroll subjects into cohorts as outlined in Section 3.1.2.

In this study, a range of single, IV doses will be evaluated during the dose escalation. The starting dose of 0.6 mg (loading dose of 0.15 mg as 0.5-hour IV infusion, followed by a maintenance dose of 0.45 mg as 5.5-hour IV infusion), was selected based on safety, PK, and PD data from a healthy volunteer (including elderly subjects) study (DS1040-A-U101).

Based on human PK data, the projected maximum (peak) observed concentration in circulating blood (C_{max}) and area under the plasma concentration-time curve (AUC) of the 0.6 mg starting dose in a typical subject with a body weight of 75 kg and a creatinine clearance of 90 mL/min are: 13.2 ng/mL and 118 ng·h/mL, respectively, which are 1.2% and 1.5% of the highest exposure achieved in healthy young subjects (mean C_{max} = 1102 ng/mL in the 12 mg 0.5-hour IV infusion dose level and mean area under the concentration-versus-time curve from time 0 extrapolated to infinity [AUC_{inf}] = 8116 ng·h/mL in the 40 mg 24-hour IV infusion dose level), and 2.6% and 10.4% of the highest exposure achieved in elderly subjects (mean C_{max} = 505 ng/mL and mean AUC_{inf} = 1135 ng·h/mL in the 6 mg 0.5-hour IV infusion dose level). Projected plasma exposure levels for planned doses are summarized in Table 3.2. Based on human biomarker data, the projected PK exposure at the starting dose of 0.6 mg will likely result in an approximately 15% reduction in clot lysis time.

The maximum dose of 9.6 mg (loading dose of 2.4 mg as 0.5-hour IV infusion, followed by maintenance dose of 7.2 mg as 5.5-hour IV infusion) was selected to achieve full effect on clot lysis time reduction. Projected C_{max} and AUC_{inf} are 212 ng/mL and 1889 ng·h/mL, respectively, which are 19% and 23% of the highest exposure achieved in healthy, young subjects, and 42% and 166% of the highest exposure achieved in elderly subjects.

Table 3.2: Projected Plasma Pharmacokinetic Parameters

Cohort	Total Dose (mg)	Loading Dose (mg) over 0.5 hours	Maintenance Dose (mg) over 5.5 hours	Simulated Plasma PK Parameters			
				C _{0.5h} (ng/mL)	C _{6h} (C _{max}) (ng/mL)	t _{max} (h)	AUC (ng·h/mL)
1	0.6	0.15	0.45	11.9	13.2	6	118
2	1.2	0.3	0.9	23.8	26.5	6	236
3	2.4	0.6	1.8	47.7	52.9	6	472
4	4.8	1.2	3.6	95.3	106	6	944
5	9.6	2.4	7.2	191	212	6	1889

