AUC = area under the plasma concentration-time curve C_{0.5h} = maximum plasma concentration at 0.5 hours; C_{6h} = maximum plasma concentration at 6 hours; PK = pharmacokinetic; t_{max} = time of maximum observed concentration.

Simulation assumptions: body weight = 75 kg, CL_{cr} = 90 mL/min

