6. STUDY PROCEDURES

A study visit schedule in tabular format is provided in Section 17.5. Unless otherwise specified, all postdose timepoints are after the start of investigational product administration.

6.1. Day 1

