6.1.1. Predose

The following assessments will be performed predose:

- Obtain written (ie, signed and dated) informed consent
- Assess inclusion/exclusion criteria
- Record medical history information (including mRS, if possible)
- Record prior/concomitant medication
- Obtain a blood sample for follicle stimulating hormone evaluation
- Obtain a serum sample for pregnancy testing in women of childbearing potential (childbearing potential is assumed in women up to 55 years of age)
- Perform a complete physical examination including weight (can be estimated by the subject, family members, or the Principal Investigator)
- Perform a non-contrast CT or MR, followed by angiography (after hemorrhagic stroke is ruled out)
- Administer the NIHSS
- Obtain supine vital sign measurements
- Perform a 12-lead ECG in triplicate
- Obtain blood samples for safety laboratory assessments (serum chemistry and hematology) (Section 9.5)
- Obtain a urine sample for urinalysis (Section 9.5)
- Obtain blood samples for PT, INR, aPTT, and fibrinogen (Section 9.5)
- Obtain PD blood sample (TAFIa activity, clot lysis, TAFI antigen, D-dimer) (Section 8.2)
- Assess subjects for adverse events
- Obtain PK blood sample

6.1.2. 0 Hour

The following assessments will be performed at 0 hour:

- Administer DS-1040b
- Start collection of urine for PK assessments

An optional PGx sample can be obtained at any time after dosing.

6.1.3. 0.5 Hours Postdose

The following assessments will be performed 0.5 hours after dosing started:

- Obtain supine vital sign measurements
- Perform a 12-lead ECG in triplicate
- Obtain blood samples for PT, INR, aPTT, and fibrinogen (Section 9.5)
- Obtain PD blood sample (TAFIa activity, clot lysis, D-dimer) (Section 8.2)
- Obtain PK blood sample

6.1.4. 3 Hours Postdose

The following assessments will be performed 3 hours after dosing:

- Obtain supine vital sign measurements
- Perform a 12-lead ECG in triplicate
- Obtain PK blood sample

6.1.5. 6 Hours Postdose

The following assessments will be performed 6 hours after dosing:

- Obtain supine vital sign measurements
- Perform a 12-lead ECG in triplicate
- Obtain blood samples for PT, INR, aPTT, and fibrinogen (Section 9.5)
- Obtain PD blood sample (TAFIa activity, clot lysis, TAFI antigen, D-dimer) (Section 8.2)
- Administer the NIHSS
- Assess subjects for adverse events
- Obtain PK blood sample

6.1.6. 9 Hours Postdose

The following assessment will be performed 9 hours after dosing:

- Obtain PK blood sample

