8.1. Pharmacokinetic (PK) Variable(s)

Blood samples for PK assessment will be collected predose and 0.5, 3, 6, 9, 12, 24, 48, 72, and 96 hours postdose. The PK parameters that will be calculated from the plasma concentrations of DS-1040a using noncompartmental analysis are shown in Table 8.1.

Table 8.1: Pharmacokinetic Parameters - Plasma

Parameter	Definition
AUC_{last} (ng·h/mL)	The area under the concentration-versus-time curve, from time 0 to the last quantifiable concentration sampling point
C_{max} (ng/mL)	Maximum (peak) observed plasma concentration
t_{max} (h)	The time of maximum observed concentration

If data permit, the following parameters will be estimated: the area under the concentration-versus-time curve, from time 0 extrapolated to infinity (AUC_{0-inf}), $t_{1/2}$, clearance, and the volume of distribution in the terminal elimination phase.

Urine collection for PK assessment will start following dosing and stop at 24 hours postdose. The PK parameters that will be calculated from the urine concentration of DS-1040b are shown in Table 8.2.

Table 8.2: Pharmacokinetic Parameters - Urine

Parameter	Definition
Ae_{0-24}	Cumulative amount of compound excreted into urine up to 24 hours
CL_R	Renal clearance
$\%Fe_{0-24}$	Cumulative percentage of dose excreted into urine up to 24 hours

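### The 6-hour PK sample marks the end of infusion but has a symmetric 30-minute tolerance, so late draws about 23% below the 6-hour value count as on time

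*Combined protocol and SAP*

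**What the plan says.** Section 6 counts time from the start of the infusion: "all postdose timepoints are after the start of investigational product administration". The regimen is a 0.5-hour loading infusion followed by a 5.5-hour maintenance infusion; for the top dose Section 3.2.1 gives "loading dose of 2.4 mg as 0.5-hour IV infusion, followed by maintenance dose of 7.2 mg as 5.5-hour IV infusion". So 6 h is the scheduled end of infusion. Table 3.2 labels C6h as Cmax, with tmax of 6 h, in all five cohorts, and its footnote calls C6h the "maximum plasma concentration at 6 hours".

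Section 8.1 fixes the sampling times: "Blood samples for PK assessment will be collected predose and 0.5, 3, 6, 9, 12, 24, 48, 72, and 96 hours postdose". Nothing is drawn between 3 h and 9 h except the 6-hour sample. Section 6.1.5 says only "The following assessments will be performed 6 hours after dosing". It does not say whether the PK sample comes before or after the infusion stops.

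Section 11.5.1 sets the tolerance. A sample breaches it when its time is off "by more than 5 minutes within the first hour, or by more than 30 minutes within the first 12 hours"; later time points have a 60-minute limit. What a breach leads to is narrow, since those values "will be listed but excluded from summary statistics at each timepoint and mean and median graphs". The synopsis has the same limits but ends "will be listed but excluded from summary statistics and mean and median graphs", without restricting the exclusion to time-point statistics. Section 8.1 defines Cmax as the highest observed concentration and tmax as its time. Section 8 requires the administration time and the exact sampling times to be recorded.

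**The concern.** A symmetric window suits a sample on a smooth part of the curve. At 6 h the curve has a corner: nearly flat while the infusion runs, steep once it stops. An early draw costs almost nothing and a late one costs a lot, so errors inside the window do not cancel. The plan allows only 5 minutes at the end of loading, the lower of the two projected concentrations (191 against 212 ng/mL at 9.6 mg), and six times as long at the end of infusion, the higher one.

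What is affected is the 6-hour concentration summary and the mean and median curves. Cmax and tmax are affected by a different route: with no other sample between 3 h and 9 h, a missed peak cannot be recovered. Cmax is summarised by dose with a geometric mean and plotted against dose, and Section 3.2.1 uses projected Cmax to place the top dose relative to earlier human exposure. With 6 or 12 active subjects per cohort and about 40 sites, differences in the timing of draws between sites may not average out.

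**Working it through.** **Inputs.** Table 3.2, 9.6 mg row (least rounding): C0.5h = 191, C6h = 212 ng/mL, AUC = 1889 ng·h/mL, for 75 kg and CLcr 90 mL/min. Loading rate 2400 µg / 0.5 h = 4800 µg/h; maintenance rate 7200 µg / 5.5 h = 1309 µg/h.

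**The plan's own figures.** 212/1102 = 19%, 1889/8116 = 23%, 212/505 = 42%, 1889/1135 = 166%, all as stated in Section 3.2.1. The table is dose-proportional (C6h is 22.0–22.1 ng/mL per mg), so the percentages below apply to every cohort. The documents give neither the simulation model nor a figure for the fall after the stop, so models were matched to the table.

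**Step 1: one compartment does not fit.** CL = 9600/1889 = 5.08 L/h. Matching C0.5h gives k = −2 ln(1 − 191 × 5.08/4800) = 0.452 per h. Then C6h = 191e^(−5.5k) + (1309/5.08)(1 − e^(−5.5k)) = 252, not 212.

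**Step 2: a limit for any linear model.** C0.5h is the response to 0.5 h at 4800 µg/h, so 0.5 h at 1309 µg/h contributes 191 × 1309/4800 = 52.1 ng/mL. By superposition, C(6.5) = C(6.5 had the infusion continued) − 52.1. Provided the continued curve would not have fallen, the drop is at most 52.1/212 = 24.6%, less whatever small rise would have followed.

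**Step 3: two-compartment fits.** With S(t) the response to a unit-rate infusion, C(t) = 4800[S(t) − S(t − 0.5)] + 1309[S(t − 0.5) − S(t − 6)]. For each intercompartmental clearance Q from 2 to 15 L/h, V1 and V2 were solved so that C0.5h and C6h match exactly. For example, Q = 5 gives V1 = 9.95 L and V2 = 10.95 L.

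| Quantity | Q = 2 to 15 L/h |
|---|---|
| Draw at 5.5 h | 1.1–2.3% below C6h |
| Draw at 6 h 05 min | 4.5–5.9% below |
| Draw at 6 h 15 min | 13–14% below |
| Draw at 6 h 30 min | 22.5–23.5% below |
| 6-hour mean, draws even over 5.5–6.5 h | 6.5–7.2% low |
| 6-hour mean, draws even over 6.0–6.5 h | 12.3–13.3% low |

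Fits with Q between 1.1 and 2 L/h give up to 24.4% at 30 minutes. As a check, Section 1.1.1.5 reports levels below 10% of the end-of-infusion value 12 hours after a 24-hour infusion. Fits with Q of 3 or more give 7–9%; Q = 2 narrowly misses at 10.6%.

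**Step 4: Cmax and tmax.** The late 6-hour value falls below an earlier sample after 8.0 minutes (Q = 2, where the 3-hour sample takes over at 93% of C6h) to 11.5 minutes (Q = 3, where the 0.5-hour sample takes over at 191/212 = 90%). From then on the Cmax error stops growing, at 1 − 0.93 = 7% or 1 − 0.90 = 10%, and tmax reads 3 h or 0.5 h. Averaged over draws, Cmax is 3–5% low for the full window and 6–8.5% low if all are 0–30 minutes late.

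**Step 5: slower elimination (assumption).** With clearance in the same fits scaled by 0.5 to 0.8, the 30-minute fall is 14–20%. Earlier samples then protect Cmax less: its error for a draw 30 minutes late is about 10–19%, and the tmax shift comes later or not at all.

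**The case against.** The strongest reply is that three stronger readings go too far, and it is right on each.

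- A reader might take 23% as the error in Cmax. It is the fall in the 6-hour concentration at the late edge of the window. In the typical subject, earlier samples cap the Cmax error at about 7–10%.
- A reader might blame the tolerance for wrong Cmax and tmax. Section 11.5.1 removes late samples only from time-point statistics and graphs. Cmax and tmax take the observed maximum whatever the tolerance, so narrowing it alone would not correct them.
- A reader might infer from Section 6.1.5, which lists PK last, that sites will draw after the stop. The list is unnumbered, and Section 6.1.3 uses a similar order, also with PK last, at 0.5 h, where 5 minutes applies. How often draws would be late is unknown.

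The 12–13% figure also assumes that no draw is early. Collection instructions are deferred to a laboratory manual, which may already specify the draw, and the recorded times would identify late samples. PK is secondary and descriptive, no passage plans a comparison of the 6-hour mean with Table 3.2, and the escalation review in Section 11.9 rests on blinded clinical and safety laboratory data.

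This limits the consequence but does not remove the point. The tolerance is written in this document, and it counts a sample about 23% low as on time at the one scheduled draw meant to catch the peak.

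**Conclusion.** The concern holds for the 6-hour concentration summaries and curves. The 30-minute window at the end of infusion gives a one-sided low bias: about 7% if draws spread evenly over the window, 12–13% if all are 0–30 minutes late, and about 23% for a single sample at the late edge. The error in Cmax (up to about 7–10% in the typical subject) and in tmax is real when the draw is more than about 8–11 minutes late. It comes from when the sample is taken and from the lack of a rule for post-infusion samples, not from the tolerance.

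These sizes assume linear kinetics, two compartments and the projected subject of 75 kg with CLcr 90 mL/min. Section 1.1.1.5 reports slower elimination in the elderly, and eligibility reaches age 80 and eGFR 60, so actual figures will differ. No stated decision rule turns on this error. It is worth correcting because the change is cheap, but it does not threaten the primary safety objective.

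**What to change.** 1. In Sections 6.1.5 and 8.1, state that the 6-hour PK sample, with its paired PD sample, is drawn in the last minutes before the infusion stops, and record the actual stop time.
2. In Section 11.5.1 and the synopsis, apply the existing 5-minute tolerance to this sample, measured from the actual end of infusion, for the time-point summaries and graphs. The largest in-window loss becomes about 5–6%, and the sample stays above the earlier ones in the projected subject.
3. Align the synopsis with Section 11.5.1 so that both restrict the exclusion to time-point statistics and graphs.
4. Flag Cmax and tmax for subjects whose 6-hour sample came more than 5 minutes after the stop, and show the Cmax summary and the dose-exposure plot with and without them. Declaring these values not evaluable could discard many in cohorts of 6 or 12 active subjects.
5. Keep every such sample at its actual time for AUC.

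The cost is a wording change, one specified draw order, one recorded time and one extra display, with no additional blood. The downside is that some late values leave the 6-hour summary.
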